14.2 Secondary Endpoint

The secondary endpoint is a comparison of the observed rate of ischemic stroke at 24 months with the CHA₂DS₂-VASc predicted rate.

14.2.1 Analysis method

[REDACTED]

14.2.2 Analysis population

The analysis will include subjects who receive an implant of an AMPLATZER LAA Occluder.

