Non-valvular AF patients have been assessed to determine the risk of stroke based on the presence of independent risk factors. In a study by Gage et al. the CHADS₂ index was shown to be a tool to predict the risk of stroke in subjects with AF⁷. The CHADS₂ score assigns one point each for the presence of congestive heart failure, hypertension, age greater than 75 and diabetes mellitus and two points for history of stroke or transient ischemic attack (TIA). The study found that AF patients who were not treated with anti-thrombotic agents had an increased risk of stroke ranging from 1.9% to 18.2% as CHADS₂ scores increase from 0 to 6.

A study by Go et al. reviewed outcome data (11,526 patients) in a large primary care setting and confirmed that thromboembolic risk increases progressively with CHADS₂ score⁸. The study also noted that oral anticoagulation with warfarin reduces the risk of stroke in most patients with the exception of those at lowest risk (CHADS₂ score of zero) and highest risk (CHADS₂ >5) for stroke. The more recently developed CHA₂DS₂-VASc risk assessment scheme⁹, which identifies truly low risk subjects, assigns two points to age ≥75 years and previous stroke, TIA or thromboembolism and one point each to congestive heart failure or left ventricular dysfunction, hypertension, diabetes, vascular disease, age between 65-74 years and female sex. A recent validation¹⁰ of these risk schemes in more than 90,000 patients without oral anticoagulation (OAC) but on aspirin showed annual ischemic stroke rates ranging from 0.6% in CHA₂DS₂-VASc = 1 to 4.8% in CHA₂DS₂-VASc = 4, and more than 12% for CHA₂DS₂-VASc = 9.

In a meta-analysis conducted by Andersen et al., warfarin was found to be superior to aspirin and placebo in reducing the risk of systemic embolism in subjects with NVAf¹¹. Hart et al. reported that adjusted dose warfarin reduces stroke by 64% (6 trials) and antiplatelet agents reduce stroke risk by 22%¹². The study also reported that risk of intracranial hemorrhage was doubled with adjusted-dose warfarin compared with aspirin.

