14.3 Descriptive Endpoints/Outcomes Measures

The following endpoints will be summarized using descriptive statistics.

Oral anticoagulant use over time:

The count and proportion of subjects using oral anticoagulants will be summarized at scheduled follow-up visit. Subjects who are implanted with the AMPLATZER LAA Occluder will be included in this analysis.

Device closure:

The number and proportion of subjects in whom device closure is achieved at the 2-month visit will be summarized. Device closure is defined as residual jet around the device \leq 5mm at the 2-month visit documented by transesophageal echocardiogram (TOE). Subjects who are implanted with the AMPLATZER LAA Occluder and in whom device closure is assessed will be included in this analysis.

Procedure duration:

Procedure duration will be summarized using descriptive statistics including mean, standard deviation, median and range. Procedure duration is defined as the time from the device delivery/device sheath is inserted into the vasculature until delivery sheath removed. Subjects who are attempted to be implanted with the AMPLATZER LAA Occluder, or have been retrospectively enrolled will be included in this analysis.

Procedure success:

The count and proportion of subjects with a successful implant will be summarized. A successful implant procedure is defined as implantation of the AMPLATZER LAA Occluder during the procedure with no serious adverse device effect prior to hospital discharge. Subjects who are attempted to be implanted with the AMPLATZER LAA Occluder will be included in this analysis.

Technical success:

The count and proportion of subjects with a successful implant will be summarized. Technical success is defined as delivery and release of the AMPLATZER LAA Occluder. Subjects who are attempted to be implanted with the AMPLATZER LAA Occluder (introduction of the delivery/device sheath into the vasculature) will be included in this analysis.

Device Thrombosis:

The count and proportion of subjects with a device thrombus will be summarized. Subjects implanted with an AMPLATZER LAA Occluder will be included in this analysis.

Transient Ischemic Attack:

Kaplan-Meier analysis will be used to estimate the rate of transient ischemic attack (TIA). Subjects who are attempted to be implanted with the AMPLATZER LAA Occluder, or have been retrospectively enrolled will be included in this analysis.

All Cause Death:

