1.4.3 Secondary Endpoint

The secondary endpoint is a comparison of the observed rate of ischemic stroke or systemic embolism at 24 months with the CHA₂DS₂-VASc predicted rate.

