2.3.2 Secondary Endpoint

The secondary endpoint will be assessed [REDACTED]

[REDACTED]

This confidential document is the property of Abbott and shall not be reproduced, distributed, disclosed or used without the express written consent of Abbott.

Statistical Analysis Plan

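### Protocol Table 3 gives a 75-year-old no age points, so CHA2DS2-VASc scores and the predicted stroke rate built on them are too low for those subjects

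*Protocol*

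**What the plan says.** Protocol 14.2 defines the endpoint: "The secondary endpoint is a comparison of the observed rate of ischemic stroke at 24 months with the" CHA2DS2-VASc predicted rate. Protocol 14.2.2 sets the population: "The analysis will include subjects who receive an implant of an AMPLATZER LAA Occluder". The analysis method is blacked out in Protocol 14.2.1, and SAP 2.3.2 is legible only as far as "The secondary endpoint will be assessed".

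The score is collected at baseline under Protocol 6.1, where Table 3 lists the items. One row gives 2 points for age above 75. Another gives 1 point for age 65 to 74. No row covers age 75.

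Protocol section 3 describes the same score differently: it "assigns two points to age ≥75 years and previous stroke, TIA or thromboembolism", with one point for ages 65 to 74.

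SAP 3.1 lists the score among the baseline variables to be summarised.

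Two further passages bear on the conditional point below. Section 3 reports a validation in which "patients without oral anticoagulation (OAC) but on aspirin showed annual ischemic stroke rates" of 0.6% at score 1, 4.8% at score 4 and more than 12% at score 9. Protocol 14.3 says of implanted subjects: "The count and proportion of subjects using oral anticoagulants will be summarized at scheduled follow-up visit".

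**The concern.** A score that rises with age should not drop from 1 point at 74 to 0 at 75 and then jump to 2 at 76. Table 3 does this if followed literally, and it contradicts the protocol's own account of the score.

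Two outputs depend on the score. The first is the predicted rate against which the observed rate is judged. A score that is too low gives a predicted rate that is too low, which makes it harder for the device to show a rate below prediction. The second is the description of the enrolled population's stroke risk, which readers will use to judge whether the results apply to their own patients.

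**Working it through.** The documents state no predicted rate, margin or power for this endpoint, so there is no figure of the plan's to reproduce.

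**Step 1. Age points under the two rules (age in whole years).**

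| Age | Table 3 | Section 3 |
|---|---|---|
| 64 | 0 | 0 |
| 65 | 1 | 1 |
| 74 | 1 | 1 |
| 75 | 0 | 2 |
| 76 | 2 | 2 |

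The rules differ only at 75, by 2 points.

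**Step 2. Effect on the mean baseline score.** If a share g of subjects is aged 75, the mean score is too low by 2g. For g = 3% to 5% that is 0.06 to 0.10 points.

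**Step 3. Effect on the predicted rate.** Inputs from section 3: 0.6% per year at score 1 and 4.8% per year at score 4. Assumptions, none of them in the documents:
- Every subject correctly scores 4, so those aged 75 are scored 2.
- The share g aged 75 is varied.
- The rate at score 2 is interpolated. Linearly it is 0.6 + (4.8 − 0.6)/3 = 2.0% per year. Geometrically it is 0.6 × (4.8/0.6)^(1/3) = 1.2% per year.
- The section 3 rates stand in for the redacted reference.

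The 24-month risk is 1 − exp(−2 × annual rate):
- score 4: 1 − exp(−0.096) = 9.15%
- score 2 at 2.0% per year: 1 − exp(−0.040) = 3.92%
- score 2 at 1.2% per year: 1 − exp(−0.024) = 2.37%

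Mean predicted rate = (1 − g) × 9.15% + g × (score 2 risk):

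| Share aged 75 | Score 2 at 2.0%/year | Score 2 at 1.2%/year | Relative fall |
|---|---|---|---|
| 1% | 9.10% | 9.09% | 0.6–0.7% |
| 3% | 9.00% | 8.95% | 1.7–2.2% |
| 5% | 8.89% | 8.81% | 2.9–3.7% |
| 8% | 8.73% | 8.61% | 4.6–5.9% |

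Reading 4.8% as an annual probability instead gives 1 − 0.952² = 9.37% at score 4. The relative falls are then almost the same.

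**Step 4. Does it matter how age is recorded?** If age is held as a fraction, the row for above 75 misses only exactly 75.0. However, ages between 74 and 75 then fall outside the 65-to-74 row on a literal reading. The gap moves but does not close.

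**The case against.** The strongest reply is that this is a typographical slip with little consequence. Section 3 states the score correctly, and the case report form, which is redacted, may already apply 75 or older. The slip touches one year of age, shifts the predicted rate by a few percent in relative terms, and works against the device. Most of this stands. It limits the size of the point but does not remove it: Table 3 is the only scoring table given to sites, and nothing legible tells them to score otherwise.

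A reader might infer something stronger: that the predicted rate describes patients off anticoagulants while the implanted population includes subjects on them, so that a device with no effect could appear to beat prediction. The ingredients are visible. The only rates given come from patients without oral anticoagulation but on aspirin, all implanted subjects are included, and anticoagulant use is tracked in them. If those rates were used unadjusted, anticoagulation would lower the observed rate and favour the device.

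The documents do not establish this. The section 3 rates are background, and no legible passage names them as the reference. The source, any censoring and any adjustment could all sit in the redacted parts of Protocol 14.2.1, SAP 2.1 and SAP 2.3.2. The device is also intended for patients seeking an alternative to long-term anticoagulation, and the share of follow-up on anticoagulants is not given. No test or sample size specific to this endpoint is visible either, so no false-positive rate can be attached to the inference.

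**Conclusion.** The Table 3 error stands on legible text and is wrong as written: at age 75 it gives 0 points where section 3 gives 2. Its effect is small and its direction is known. With 3 to 5% of subjects aged 75, all otherwise at score 4, the mean predicted 24-month rate falls from about 9.15% to 8.8–9.0%, against the device. The age share, the uniform score and the interpolated rate at score 2 are assumptions. The contradiction itself rests on none of them. Whether any subject has actually been mis-scored depends on the case report form, which cannot be seen.

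The anticoagulant mismatch is a conditional point only. It would push in the opposite direction to the age error, but whether it exists and how large it is cannot be determined from the documents.

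**What to change.** 1. Change the upper age row of Table 3 to 75 or older, to agree with section 3. In the SAP, derive the score for the secondary comparison and for the SAP 3.1 summary from recorded age and the component items, not from a site-entered total. The cost is a one-character correction and a re-derivation for subjects aged 75.

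2. Confirm that SAP 2.3.2 names the source of the predicted rate and says how anticoagulated follow-up is handled. If it already does, nothing more is needed. If the source is a cohort off anticoagulants and there is no adjustment, add a sensitivity version that accounts for follow-up on anticoagulants where medication data allow, and report it beside the unadjusted result.

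The sensitivity version has two limits. For retrospectively enrolled subjects, Protocol section 6 asks for baseline, echo and adverse event forms to be completed from records. It does not require medication data for the time between implant and consent, so exposure may be incomplete. Starting or stopping an anticoagulant may also itself be related to stroke risk, which is why this version should stand beside the main comparison and not replace it.

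3. While SAP 2.3.2 is open, reconcile the event definition. SAP 1.4.3 reads "The secondary endpoint is a comparison of the observed rate of ischemic stroke or systemic embolism at 24 months with the" predicted rate, which adds systemic embolism to the Protocol's ischemic stroke. This is separate from the age error, but the predicted rate must refer to the same event as the observed one.

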14.3 Descriptive Endpoints/Outcomes Measures

The following endpoints will be summarized using descriptive statistics.

Oral anticoagulant use over time:

The count and proportion of subjects using oral anticoagulants will be summarized at scheduled follow-up visit. Subjects who are implanted with the AMPLATZER LAA Occluder will be included in this analysis.

Device closure:

The number and proportion of subjects in whom device closure is achieved at the 2-month visit will be summarized. Device closure is defined as residual jet around the device \leq 5mm at the 2-month visit documented by transesophageal echocardiogram (TOE). Subjects who are implanted with the AMPLATZER LAA Occluder and in whom device closure is assessed will be included in this analysis.

Procedure duration:

Procedure duration will be summarized using descriptive statistics including mean, standard deviation, median and range. Procedure duration is defined as the time from the device delivery/device sheath is inserted into the vasculature until delivery sheath removed. Subjects who are attempted to be implanted with the AMPLATZER LAA Occluder, or have been retrospectively enrolled will be included in this analysis.

Procedure success:

The count and proportion of subjects with a successful implant will be summarized. A successful implant procedure is defined as implantation of the AMPLATZER LAA Occluder during the procedure with no serious adverse device effect prior to hospital discharge. Subjects who are attempted to be implanted with the AMPLATZER LAA Occluder will be included in this analysis.

Technical success:

The count and proportion of subjects with a successful implant will be summarized. Technical success is defined as delivery and release of the AMPLATZER LAA Occluder. Subjects who are attempted to be implanted with the AMPLATZER LAA Occluder (introduction of the delivery/device sheath into the vasculature) will be included in this analysis.

Device Thrombosis:

The count and proportion of subjects with a device thrombus will be summarized. Subjects implanted with an AMPLATZER LAA Occluder will be included in this analysis.

Transient Ischemic Attack:

Kaplan-Meier analysis will be used to estimate the rate of transient ischemic attack (TIA). Subjects who are attempted to be implanted with the AMPLATZER LAA Occluder, or have been retrospectively enrolled will be included in this analysis.

All Cause Death:

Kaplan-Meier analysis will be used to estimate the rate of death. Subjects who are attempted to be implanted with the AMPLATZER LAA Occluder, or have been retrospectively enrolled will be included in this analysis.

Major Bleeding:

Kaplan-Meier analysis will be used to estimate the rate of major bleeding events. Major bleeding is defined as Type 3 or greater based on BARC. Subjects who are attempted to be implanted with the AMPLATZER LAA Occluder, or have been retrospectively enrolled will be included in this analysis.

Reporting:

The following data will be summarized and reported annually to Health Canada.

- Investigator sites and enrollment status
- Demographic and baseline characteristics
- Serious Adverse Events
- Procedural results (procedure success, implanted device size, procedure duration)
- Device closure rates
- Oral anticoagulant use

14.4 Compromising Factors

This is an observational post approval study evaluating real-world outcomes in subjects undergoing implant with an AMPLATZER LAA Occluder. The study endpoints and analysis populations will appropriately characterize safety of the procedure and long-term effectiveness of the device. There are no known or foreseeable factors that may compromise the outcome of the clinical investigation or the interpretation of results.

15. Document Retention

After the termination of the study, the principal investigator will maintain all clinical study documents on file at the site for the minimum number of years required per local laws, or 2 years following study completion, whichever is longer duration.

16. Amendments to the Clinical Protocol

Study related documents such as, protocol, eCRFs (

Appendix F: Case Report Forms) informed consent form (**Appendix E:** Sample Informed Consent) and other subject information, or other clinical study documents will be amended as needed throughout the clinical study, and a justification statement will be included with each amended section of a document. Proposed amendments to the protocol will be agreed upon between the Sponsor and the coordinating investigator (if applicable).

The protocol, the subject's informed consent form and amendment notification will be submitted for review and approval by the local IRB/EC and regulatory authorities (as applicable). The version number and date of amendments will be documented (**Appendix B:** Protocol Revision History).

The amendment will identify the changes made, the reason for the changes and if it is mandatory or optional to implement the amendment. Any amendment affecting the subject requires that the subject be informed of the changes, and a new consent be signed and dated at the subject's next follow up.

17. Outsourcing of Sponsor Duties and Functions

The Sponsor does not anticipate transferring any duties and functions related to the clinical study, including monitoring, to an external organization (such as a contract research organization or individual contractor). If outsourcing does occur, the ultimate responsibility for the quality and integrity of the clinical study will reside with the Sponsor. All requirements applying to the Sponsor will also apply to the external organization inasmuch as this organization assumes the clinical study related duties and functions of the Sponsor.

18. Investigation Suspension or Termination

18.1 Premature Termination

The Sponsor reserves the right to stop the study at any stage, with appropriate written notice to the investigator.

Possible reasons for early termination of the study by the Sponsor, either at local, national or international level, may include, but are not limited to:

- Sponsor's decision
- Request from regulatory authorities
- Request of EC(s)
- Concern for subject safety and welfare
- Failure to secure subject informed consent prior to any protocol activity
- Failure to report unanticipated adverse device effects within 72 hours to SJM and the EC
- Repeated non-compliance with this clinical protocol or the clinical trial agreement
- Inability to successfully implement this clinical protocol
- Violation of the Declaration of Helsinki (refer to **Appendix C**)
- Violation of applicable national or local laws and regulations
- Falsification of data, or any other breach of ethics or scientific principles

In such events, the study will be terminated according to applicable regulations. The investigator may also discontinue participation in the clinical study with appropriate written notice to the Sponsor. Should either of these events occur, the investigator should provide a written statement as to why the premature termination has taken place, and notify the EC and/or the CA (if applicable). Follow-up for all enrolled subjects will be per center standard of care.

A principal investigator, EC, or regulatory authority may suspend or prematurely terminate participation in a clinical study at the investigational sites for which they are responsible.

18.2 Study Conclusion

The study will be concluded when:

- All sites are closed AND
- The final report generated by Abbott has been provided to sites or Abbott has provided formal documentation of study closure

19. Publication Policy

The results of the clinical study are planned to be submitted for publication. If a principal investigator will be involved in publishing the data, a publication agreement will be signed between the PI and Sponsor either as a separate publication agreement or within the clinical trial agreement.

The investigator or site may not publish any information that the Sponsor believes to be confidential information. The publication of the initial results of the AMPLATZER LAA Occluder Post Approval Study shall be subject to review and release of the Sponsor's publication committee, which shall confer with the site regarding such publication.

Publication guidelines will be followed according to the International Committee of Medical Journal Editors (ICMJE). This study will also be posted on ClinicalTrials.gov and results will be posted on ClinicalTrials.gov as required.

20. Bibliography

Appendix A: Abbreviations

Abbreviation	Term
ACP	Amplatzer Cardiac Plug
AE	Adverse Event
AF	Atrial Fibrillation
AP	Asia-Pacific
ANZ	Australia-New Zealand
CA	Competent Authority
CE	Conformité Européenne
CEC	Clinical Events Committee
CP	Clinical Protocol
CRF	Case Report Form
CNS	Central Nervous System
CT	Computed Tomography
DMP	Data Management Plan
EC	Ethics Committee
ECG	Electrocardiogram
eCRF	Electronic Case Report Form
EDC	Electronic Data Capture
EMEA	Europe, Middle East, Africa
EP	Electrophysiologist
IB	Investigator's Brochure
IC	Interventional Cardiologist
ICMJE	International Committee of Medical Journal Editors
IFU	Instructions For Use
INR	International Normalized Ratio
ISO	International Organization for Standardization
LAA	Left Atrial Appendage
LAAO	Left Atrial Appendage Occlusion
MRI	Magnetic Resonance Imaging
mRS	Modified Rankin Scale
NCA	National Competent Authority
NVAF	Non-Valvular Atrial Fibrillation
OAC	Oral Anticoagulant
PI	Principal Investigator
SADE	Serious Adverse Device Effect
SAE	Serious Adverse Event
SC	Steering Committee
SJM	St. Jude Medical, Inc.
TIA	Transient Ischemic Attack
TOE	Transoesophageal Echocardiography
WMA	World Medical Association

Appendix B: Protocol Revision History

Appendix C: Declaration of Helsinki

The 2013 version of the Declaration of Helsinki is available at:

[figure not shown]
<http://www.wma.net/en/20activities/10ethics/10helsinki/>. Please check the website during the course of the study for updated revisions.

[figure not shown]

Appendix F: Case Report Forms

[Redacted]

[Redacted]

Appendix G: Modified Rankin Scale (mRS)

Subject Identifier: _____

Rater Name: _____

Date: _____

Score	Description
0	No symptoms at all
1	No significant disability despite symptoms; able to carry out all usual duties and activities
2	Slight disability; unable to carry out all previous activities, but able to look after own affairs without assistance
3	Moderate disability; requiring some help, but able to walk without assistance
4	Moderately severe disability; unable to walk without assistance and unable to attend to own bodily needs without assistance
5	Severe disability; bedridden, incontinent and requiring constant nursing care and attention
6	Dead

TOTAL (0-6): _____**Comments:**

